6.1.2 Sample size

An estimated 86 patients are anticipated to be enrolled at one US site. The sample size was initially estimated for a two-sided hypothesis test (two-sample equal-variance t-test) with a significance level of 0.05 comparing total hospital time (number of days) between the pre- and post-periods with 80% power. Assuming an average hospital length of stay of 4.0 days (inclusive of all enrolled subjects), with a standard deviation of 3.0 days, and a 2 day reduction in length of stay between the pre- and post-periods, it was estimated that 37 subjects in each arm of the trial (total enrollment of 74) would be required to demonstrate a mean reduction in hospital stay of 2 day. The final enrollment, including adjustments for attrition came to 86 subjects (43 patients in each period).

The average length of stay and variance for the site was determined after an estimated 25 subjects were enrolled in the pre-period. The sample size was confirmed with the interim analysis and the enrollment of 86 patients will be targeted.

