6.2.4 Outcomes

6.2.4.1 Primary Outcomes

Primary Outcome: Infection-related Total Admitted Hospital Days

Infection-related total admitted hospital days will be calculated by two methods for the FAS population. First, LOS will be calculated by inpatient only stays and second, LOS will be calculated by inpatient stays including time spent in prolonged observation status (> 1 day). Descriptive statistics for the primary

[REDACTED]

outcome will be shown in a table by initial care, follow-up, and overall for the pre-period and post-period, and depicted graphically overall using box plots. Patient counts and percentages will be given for the primary outcome (e.g., 0 day, 1 day ... > 5 days). Descriptive statistics in the table will be repeated by all patients and patients who complete the study for comparison.

The primary analysis will consist of Hypothesis testing using a two sided (two sample equal-variance) t-test, with a significance level of 0.05, comparing the difference in total time (in days) spent in hospital between the pre- and post-periods. Violations of assumptions for the t-test in the data will be checked for. An appropriate alternative method will be selected if a major violation to an assumption is present, such as the Mann-Whitney U test². Overall differences in descriptive statistics between the pre- and post-periods for infection-related total admitted hospital days will be reported.

Because the baseline characteristics of the pre-period may differ from those of the post-period, a secondary analysis using a multivariate regression analyses, specifically a generalized linear mixed model (GLMM), [REDACTED]. As the outcome is expected to be heavily right skewed, the number of hospital days will be modeled assuming a negative binomial distribution with log link. If the model does not converge or fit, an alternate distribution will be selected. This model will assume mutual independence between the sites. Similar to above, the multivariate analysis will be completed for the primary outcome for inpatient stays only as well as including time spent under observation, as well as for all patients and patients who complete the study for comparison.

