Figure 2 Box Plot of Infection-Related Hospitalization Time During Initial Care and Follow-up for Patients Completing the Study by Pre- and Post-period: Full Analysis Set

[figure not shown]
Listing 1 Patient Disposition: Enrolled Set§¶

- Listing 2 Patients Who Did Not Meet Inclusion or Exclusion Criteria: Patients Excluded from Enrolled Set §
- Listing 3 Patient Demographics at Baseline: Enrolled Set§
- Listing 4.1 Medical History at Baseline Visit: Enrolled Set, Part 1§
- Listing 4.2 Medical History at Baseline Visit: Enrolled Set, Part 2§
- Listing 4.3 Medical History at Baseline Visit: Enrolled Set, Part 3§
- Listing 4.4 Medical History at Baseline Visit: Enrolled Set, Part 4§
- Listing 5.1 Infection Characteristics: Enrolled Set, Part 1§
- Listing 5.2 Infection Characteristics: Enrolled Set, Part 2§
- Listing 6 Antibiotic Usage: Enrolled Set §
- Listing 7 Prior Non-Antibiotic Usage for Chronic Conditions Reported at Baseline: Enrolled Set§
- Listing 8 Hospitalization, ED and Observation Unit Visits: Enrolled Set §
- Listing 9 Hospitalization Length of Stay: Enrolled Set §
- Listing 10 Other Healthcare Visits: Enrolled Set§
- Listing 11 SF-12 Questionnaire at Baseline and Day 14: Enrolled Set
- Listing 12 Patient Satisfaction Survey at Day 14: Enrolled Set
- Listing 13 WPAI at Day 14: Enrolled Set
- Listing 14 Surgical Interventions and Procedures: Enrolled Set§
- Listing 15 Adverse Events: Enrolled Set§
- Listing 16 Laboratory Results: Enrolled Set§
- Listing 17 Microbial Assessments: Enrolled Set§
- Listing 18 Vital Signs and Physical Examination at Follow-up: Enrolled Set§

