9.0 Appendices

Appendix B: Derived Variables

[figure not shown]
Analysis Section (Visit)	Variable (Units)	Definition
General (Baseline)	Enrollment date	Informed consent date
General (Baseline)	Baseline date	Hospital admission date at initial episode of care
General (Initial Care)	Initial care indicator	If enrollment date \leq date \leq enrollment date + 13 days then = Yes Else = No
General (Follow-up)	Follow-up indicator	If enrollment date + 14 \leq date \leq enrollment date + 43 days then = Yes Else = No
Demographics (Baseline)	Age (years)	Round down to nearest integer((Initial hospital admission date - date of birth + 1)/365.25), when both dates are available.
Demographics (Baseline)	BMI	weight (kg)/ [height(m)] ² Where necessary, height and weight will be converted to proper units.
Infection Characteristics (Baseline)	CCI	Will be scored as described in Appendix C. Includes variables for raw score and 10 year survival probability.
Infection Characteristics (Baseline)	Immunocompromised	=YES if any of the following at baseline: 
 - Diabetes mellitus - Leukemia - Malignant lymphoma
Infection Characteristics (Baseline)	Fever	If temperature > 38 ° C then =Yes Else =No
Infection Characteristics (Baseline)	SIRS Criteria Met	SIRS criteria include abnormalities in temperature, heart rate, respiration, and white blood cell count. Specifically included are:

[figure not shown]
Analysis Section (Visit)	Variable (Units)	Definition
		
 • Fever of more than > 38.0°C or hypothermia with temperature < 36.0°C • Tachycardia with heart rate > 90 beats/minute or • Tachypnea with respiratory rate of > 20 breaths/minute or PaCO₂ of less than 32mmHg • Abnormal white blood cell count: leukocytosis >12,000/microliter, leucopenia <4,000/microliter, or >10% immature cells (bands).^{3,4} 
If 2 or more criteria present = Yes Else = No

Antibiotic Medications (Initial Care and Follow-up)	Days Received Antibiotic Medication	Σ (Medication end date – Medication start date +1), when both dates are available. If dates overlap (e.g., end date and next start date are identical) then subtract 1 from summation for each occurrence.

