Primary and Secondary Outcomes (All visits)	Hospitalization LOS (days)	
For all-cause: Σ (Hospitalization end date – Hospitalization start date +1), when both dates are available. If ongoing at end of study or discontinuation date, use study completion date or discontinuation date as end date. For outcomes, LOS will be computed two ways: only inpatient hospitalizations visits and inpatient hospitalizations visits with prolonged observation status (e.g., time in observation status exceeds 1 day). For infection-related:

[figure not shown]
Analysis Section (Visit)	Variable (Units)	Definition
		Subset all-cause hospitalization time for patients with infection-related hospitalization stays
Primary and Secondary Outcomes (End of Study Visit)	Completers Flag	
If "Did the patient complete the study?" = 1 on the end of study visit CRF page and date of study completion does not equal missing, then =Yes, Else = No
 
This flag will be used to repeat certain primary and secondary outcomes that could be influenced by early discontinuation (e.g., LOS)

Secondary Outcomes (Follow-up)	Response to Therapy at End of Therapy Visit	
The response will be categorized as a "Complete Response" if at the day 10-14 visit there is a reduction in pain or no pain, tenderness, nor fever and the primary lesion area has reduced in size.
 
Else, the response will be categorized as a "Partial Response" if at the day 10-14 visit there is a reduction in pain score or no pain, tenderness, nor fever and the primary lesion area remained the same size.
 
Else, the response will be categorized as a "Failure."

Secondary Outcomes (Follow-up)	WPAI	Scores and coded variables will be derived as described in Appendix D.
Secondary Outcomes (Initial Care and Follow-up)	SF-12	SF-12 sub-scores and total scores will be compiled using the Health Outcomes Scoring Software 5.0 by QualityMetric Inc. Further detail is given in Appendix E.
Adverse Events (Baseline, Initial Care and Follow-up)	Highest severity AE	Severity of most severe AE for the patient with order of severity: Severe>Moderate>Mild Patients who only have AEs reported with missing severity,

Analysis Section (Visit)	Variable (Units)	Definition
		highest severity AE will be reported as missing

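### The length-of-stay formula counts a date twice when two recorded stays meet on it, and the SAP's shared-date correction covers only antibiotic days, exactly only for one-day overlaps

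*SAP*

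**What the plan says.** In SAP Appendix B, the row for hospitalization length of stay (LOS) defines the all-cause value as a sum over stays. Each stay contributes its end date minus "Hospitalization start date +1), when both dates are available". Infection-related LOS, the primary outcome, is taken as a subset of this quantity and so inherits the formula. The row does not say what happens when two stays share a date.

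The row just before it, for days on antibiotics, uses the same kind of sum and adds a correction: "If dates overlap (e.g., end date and next start date are identical) then subtract 1 from summation for each occurrence".

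SAP 6.2.4.1 calculates the primary outcome in two ways, once from inpatient stays alone and once so that "LOS will be calculated by inpatient stays including time spent in prolonged observation status (> 1 day") is counted as well. Among the outputs in SAP 7.0, Listing 8 is titled "Hospitalization, ED and Observation Unit Visits: Enrolled Set", so observation visits are recorded as a kind of visit alongside hospitalizations. The primary test is a t-test "comparing the difference in total time (in days) spent in hospital between the pre- and post-periods".

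**The concern.** The +1 makes each stay an inclusive count of calendar dates, which is a sound convention for a single stay. It is not additive when one stay ends on the date the next begins, because both stays claim that date. The antibiotic row shows that the authors knew of the problem, yet the primary outcome has no such rule.

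The situation is foreseeable. In the observation-inclusive count, a patient who moves from prolonged observation to inpatient status has two adjoining intervals. In either count, a same-day transfer between hospitals or a same-day readmission does the same. If such boundaries are more frequent in one period than the other, the primary difference shifts with them. Two programmers could also derive different primary outcomes from the same data, depending on whether they merge adjoining records.

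For antibiotic days the stake is smaller, since SAP 6.2.6 plans only descriptive summaries. Post-period patients receive a single dalbavancin dose (protocol 3.2.2), while usual care is the investigator's choice (protocol 3.2.1). Overlapping courses are therefore more likely in the pre-period, so an inexact rule would probably not act equally on the two periods.

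**Working it through.** **The plan's own figure.** SAP 6.1.2 (and protocol 6.3) bases the sample size on a "two-sided hypothesis test (two-sample equal-variance t-test") with alpha 0.05, 80% power, SD 3.0 days and a reduction from 4.0 to 2.0 days. The standardized effect is 2/3. The noncentral t solution is 36.31 per period, rounded up to 37, which matches the plan. Power is 0.808 at 37 and 0.863 at 43 per period. This point does not put the sample size in question.

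**LOS on example stays** (formula: sum of end - start + 1)

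- Observation days 1-3, then inpatient days 3-5: (3 - 1 + 1) + (5 - 3 + 1) = 3 + 3 = 6. Distinct dates: 5.
- Inpatient days 1-3, then a transfer stay on days 3-6: 3 + 4 = 7. Distinct dates: 6.

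Each shared date adds exactly 1 day.

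**Antibiotic days on example courses** (same sum, minus 1 per overlap)

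- Days 1-5, then days 5-9 (the one-day overlap the rule illustrates): 5 + 5 - 1 = 9. Distinct dates: 9. The rule is exact.
- Days 1-5 and 4-8: 5 + 5 - 1 = 9. Distinct dates: 8.
- Two drugs together on days 1-5: 5 + 5 - 1 = 9. Distinct dates: 5.

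If an occurrence means each overlapping date, the last two become 10 - 2 = 8 and 10 - 5 = 5, both correct. The text does not say that this is meant.

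**Effect on the primary difference.** Let q be the share of patients in a period with one double-counted date. That period's mean rises by q, so the difference (pre minus post) is 2 + q_pre - q_post. If the extra day is independent of the rest of the stay, the pooled SD is sqrt(9 + [q_pre(1 - q_pre) + q_post(1 - q_post)]/2). The documents give no value for q; the values below are assumptions.

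| q_pre | q_post | Difference (days) | SD | Power at 43 per period |
|---|---|---|---|---|
| 0 | 0 | 2.0 | 3.000 | 0.863 |
| 10% | 10% | 2.0 | 3.015 | 0.860 |
| 30% | 30% | 2.0 | 3.035 | 0.856 |
| 20% | 0 | 2.2 | 3.013 | 0.917 |
| 0 | 20% | 1.8 | 3.013 | 0.782 |

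**The case against.** The strongest reply is that double counting depends on how records are stored. It needs two records meeting on one date, and neither document says whether a transfer or a change from observation to inpatient status is entered as one record or two. Exposure is also narrow. There is one site, patients are enrolled after admission, and observation time counts only in the second calculation and only when it exceeds one day. Moves to intensive care raise no problem, since SAP 4.3 and 6.2.2 treat an ICU admission as part of a hospitalization. The formula is the same in both periods, so any error may largely cancel. All of this stands and limits the size of the point. It does not remove it: observation is a separate visit type that the SAP adds to inpatient time, and the formula as stated gives a wrong value when the two meet.

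On antibiotic days, the correction can be read as once per overlapping date, which would make the two-drug examples right. Its own illustration, one course ending on the date the next begins, suggests the narrower reading, but the wording permits both.

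A reader might also infer that the +1 itself biases the adjusted analysis, in which "the number of hospital days will be modeled assuming a negative binomial distribution with log link", because a constant does not cancel in a ratio. The documents do not support that. Inclusive calendar days are a legitimate measure of admitted days, and their ratio is the right ratio for that measure. The SAP does not say whether the planned 4.0 and 2.0 days are calendar days or elapsed days, so no shift from a planned ratio can be shown. Counting distinct dates would return the same value as the present formula for every patient with a single stay.

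**Conclusion.** The point holds as a minor defect in two stated derivations. The LOS formula counts a date twice whenever two separately recorded stays share it. The antibiotic-day correction is, on its plain reading, exact only for one-day overlaps.

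The error is exactly one day per shared hospital date. Its effect on the primary comparison is unknown, because the frequency of shared dates is not given. With equal shares of 10% to 30% in both periods, the planned difference stays at 2.0 days and power falls only from 0.863 to between 0.856 and 0.860. With an assumed 20% in one period only, the difference becomes 2.2 days (pre-period) or 1.8 days (post-period). These figures assume at most one shared date per patient and independence from the rest of the stay.

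A reader should not infer that the primary result is known to be biased, or in which direction. The documents give no reason to expect shared hospital dates more often in one period than the other.

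**What to change.** In SAP Appendix B, define both LOS calculations as the number of distinct calendar dates covered by at least one qualifying stay, after merging adjoining and overlapping records. Define antibiotic days likewise, as the number of distinct dates covered by at least one antibiotic. State the calendar-date convention once so that it applies to both variables.

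The new definition equals the present formula wherever no dates are shared. It needs no new data and leaves the sample size as it is. The cost is two changed rows in Appendix B and a short piece of code.

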3.2.2 Post-period

During the post-period, all enrolled subjects will receive treatment for ABSSSI with dalbavancin at each participating site. Dalbavancin will be administered as a single IV dose of 1500 mg over 30 minutes (1125 mg over 30 minutes if CrCl <30 mL/min, for those not on regularly scheduled dialysis).¹² Dalbavancin will be provided to sites by study sponsor.

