Infection-related healthcare visits (e.g., hospitalizations, ED visits, other outpatient visits) due to PICC line or central line used to administer antibiotic therapy during initial care and follow up	Unexpected visits due to PICC line (i.e. complications)
	Expected visits due to PICC line (i.e. initial placement, monitoring of PICC line)
	All visits due to PICC line (both unexpected and expected visits)
Response to treatment at end of therapy visit	Response to treatment (healthcare provider assessment) comparing response at the 10-14 day visit (end of therapy visit). Response to treatment will be defined

[figure not shown]

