reason, admission to the ICU and primary reason, ED visits or other outpatient visits (e.g., infusion center and physician’s office) and primary reason, use of dialysis, use of any medications for chronic diseases and specifically use of an antibiotic medication, prior antibiotic treatment failure (determined by discontinuation of treatment due to worsening or recurrent ABSSSI or the occurrence of an adverse event related to the antibiotic), and receipt of wound care for the presenting infection.

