4.3 Secondary Outcomes

Secondary outcomes will be assessed during initial care (the date of enrollment to day 14) and/or follow-up (30 days after initial care), and include:

[figure not shown]
[figure not shown]
Measure	Definition	Period of Assessment
Total admitted hospital days	Total length of stay (LOS) of all hospitalizations during the 44 days of the study (including initial hospitalization)	Initial care and follow-up
Infection-related major surgical interventions that required operating room time	Number of all, unexpected and expected infection-related major surgical interventions that required operating room time	Initial care and follow-up
Infection-related hospitalizations	Number of infection-related hospitalizations	Initial care and follow-up
Infection-related hospitalizations that resulted in admission to ICU	Number of infection-related hospitalizations resulting in admission to the ICU.	Initial care and follow-up
All-cause hospitalizations in the 30 days following discharge from the initial hospitalization	Number of all hospitalizations for patients after initial hospitalization discharge	Overall, including Initial care and follow-up
Infection-related ED visits	Number of all, unexpected and expected infection-related ED visits	Initial care and follow-up

[figure not shown]
Measure	Definition	Period of Assessment
Infection-related outpatient healthcare visits (e.g., physicians' office visits, ED visits, infusion center visits, home health visits)	Number of all, unexpected and expected infection-related outpatient healthcare visits, generated for all patients and repeated by site.	Initial care and follow-up
Use of PICC line or central line to administer antibiotic therapy	Number of PICC line or central line placement for antibiotic therapy	Initial care and follow-up
Infection-related healthcare visits (e.g., hospitalizations, ED visits, other outpatient visits) due to PICC line or central line used to administer antibiotic therapy	Number of all, unexpected and expected infection-related healthcare visits due to PICC line or central line used to administer antibiotic therapy	Initial care and follow-up
Response to treatment at end of therapy visit	Response to treatment will be defined through an assessment of erythema and the absence of fever at 10-14 days and will be categorized as a complete response, partial response, or failure.	Initial care

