6.1 General Considerations

6.1.1 Analysis populations

Enrolled Set

The enrolled set consists of all patients who have signed informed consent and met all study eligibility criteria. Data will be summarized on disposition and baseline characteristics. Output will be summarized by study period (pre-period vs. post-period). All data listings will be reported for the enrolled set unless specified in Section 5.2.

Full Analysis Set

The full analysis set (FAS) population consists of all enrolled patients. Additionally, patients in the pre-period must receive at least one dose of antibiotics and patients in the post-period must receive at least one dose of dalbavancin for inclusion. All patients in the pre-period and post-period will be analysed. Data will be summarized by study period.

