Use of PICC line, central line or no line to administer antibiotic therapy will be displayed in tables by initial care, follow-up, and overall for the pre-period and post-period for the FAS population. Patient counts and percentages will be presented. Differences in proportions between the pre- and post-period will be analyzed by a chi-square test or Fisher's exact test, as appropriate.

Secondary Outcomes: Infection-related Healthcare Visits Due to PICC Line or Central Line Used to Administer Antibiotic Therapy

Infection-related healthcare visits due to PICC line or central line used to administer antibiotic therapy will be displayed in tables by initial care, follow-

up, and overall by the pre-period and post-period for the FAS population. Patient counts and percentages will be reported for none, any, 1, 2, and ≥ 3 infection-related outpatient healthcare visits. These categories will be repeated for all, expected, and unexpected outpatient healthcare visits. Differences in proportions between the pre- and post-period will be analyzed by a chi-square test or Fisher's exact test, as appropriate, and given with asymptotic 95% CIs.

Secondary Outcomes: Response to Treatment at End of Treatment Visit

Response to treatment at end of treatment visit will be a derived variable and further detail for the derivation is given in Appendix B. Response to treatment at end of treatment visit (complete, partial, failure) will be displayed in tables for the pre-period and post-period for the FAS population. Patient counts and percentages will be presented. Differences in proportions between the pre- and post-period will be analyzed by a chi-square test or Fisher's exact test, as appropriate.

Secondary Outcomes: Serious Adverse Events

Serious adverse events will be reported in a table as presented in section 6.2.7. No formal hypothesis testing will take place.

Secondary Outcomes: Patient Satisfaction with Care

Descriptive statistics for the patient satisfaction questionnaire will be reported within a table by the pre-period and post-period for the FAS population. No scoring or formal hypothesis testing will take place. A listing will display the date of visit the assessment occurred, questions answered, and the response to each question for each patient.

Secondary Outcomes: Patient Work and Productivity Loss

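### The day 10-14 response rule ignores what happened since enrollment, so a patient whose infection worsened and was then rescued can be scored a Complete Response

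*SAP*

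**What the plan says.** SAP 6.2.4.2 makes response a derived variable and names the place that governs it: "Response to treatment at end of treatment visit will be a derived variable and further detail for the derivation is given in Appendix B". Appendix B then sets three categories.

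- **Complete Response:** judged at the day 10-14 assessment, when "there is a reduction in pain or no pain, tenderness, nor fever and the primary lesion area has reduced in size".
- **Partial Response:** essentially the same signs, with the primary lesion unchanged in size.
- **Failure:** everyone else.

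The SAP 4.3 outcome table describes the endpoint more briefly: "Response to treatment will be defined through an assessment of erythema and the absence of fever at 10-14 days". Protocol Table 3 (section 4.1.2) calls it "Response to treatment (healthcare provider assessment) comparing response at the 10-14 day visit (end of therapy visit"; the rest of that definition is cut off in the text available to this review.

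On who is analysed, SAP 6.1.1 requires only one dose of antibiotic in the pre-period, and "patients in the post-period must receive at least one dose of dalbavancin for inclusion".

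For history before enrollment, SAP 4.1 has an item for earlier failure of an antibiotic, which is "determined by discontinuation of treatment due to worsening or recurrent ABSSSI or the occurrence of an adverse event related to the antibiotic".

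**The concern.** The endpoint is labelled response to therapy and has a Failure category, yet it reads only the clinical findings at one visit, compared with an earlier value for pain and lesion size. Events between enrollment and that visit do not enter. Improvement produced by a second antibiotic, an unplanned operation or a readmission is thus credited to the period's initial treatment. Before enrollment, the SAP would call a course stopped for worsening infection a treatment failure. On study, the same course can be a full success.

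In the text supplied, this is the only outcome that grades clinical response directly. Readers will turn to it when asking whether shorter stays came at a clinical cost. The report could also be hard to reconcile: one patient could add readmission days to the primary outcome and also be listed as a complete responder.

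**Working it through.** **The plan's own figure.** No response rate, rescue rate or power is stated for this endpoint. The only figure used here is the denominator, from the primary-outcome sample size (Protocol 6.3, SAP 6.1.2): SD 3.0 days, difference 2 days, two-sided 0.05, 80% power.

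- Normal approximation: 2 × (1.960 + 0.842)² × 3² / 2² = 35.3, so 36 per arm.
- Two-sample t-test: 36.3, so 37 per arm, as stated. Enrollment is then raised to 43 per period for attrition.

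**Reading the rule.** Take a patient whose infection worsens on day 3, who is given another antibiotic for that reason, and who at day 12 has a smaller lesion and no pain, tenderness or fever.

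1. *In the analysis set?* Yes. One qualifying dose suffices (SAP 6.1.1), and Protocol 3.5 does not list lack of response by itself as a reason for discontinuation.
2. *Complete Response?* Yes. The Complete Response sentence can be parsed in more than one way, but this patient meets it on any of them.
3. *Does another section override this?* No. SAP 4.3 refers to erythema and fever only. SAP 6.2.6 tabulates on-study antibiotics, and SAP 6.2.4.2 tabulates unexpected surgery and infection-related hospitalizations. None is linked to response. The antibiotic change that Protocol 3.5 foresees for Gram-negative, anaerobic or fungal infection is not mapped to a response category either.

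If the lesion had not shrunk, or the symptom criteria were not met, the same patient would not be Complete.

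**Size per patient.** 1/43 = 2.3 percentage points of one period's rate. If only 37 were assessed, 1/37 = 2.7 points.

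**Illustration (all counts assumed).** Suppose the current rule gives 36/43 = 83.7% Complete Response in each period, a difference of 0, and some of those 36 had been rescued.

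| Rescued, pre v post | Pre, rescue = Failure | Post, rescue = Failure | Post minus pre |
|---|---|---|---|
| 2 v 2 | 34/43 = 79.1% | 34/43 = 79.1% | 0 |
| 4 v 4 | 32/43 = 74.4% | 32/43 = 74.4% | 0 |
| 1 v 4 | 35/43 = 81.4% | 32/43 = 74.4% | -7.0 points |
| 2 v 6 | 34/43 = 79.1% | 30/43 = 69.8% | -9.3 points |
| 6 v 2 | 30/43 = 69.8% | 34/43 = 79.1% | +9.3 points |

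Equal rescue lowers both rates and leaves the difference alone. Unequal rescue moves the difference either way. Rescue counts of 2 v 6 of 43 are themselves compatible with chance: Fisher p = 0.27; difference 9.3 points, Wald 95% CI -2.8 to 21.4.

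**The case against.** The best defence is that this is a pragmatic comparison of a pathway with usual care. How the patient is at day 10-14, whatever was done in between, is a legitimate treatment-policy question. Usual care is the investigator's choice with discretionary duration, so a change of drug is not in itself a failure. The events in question are not lost: unexpected surgery, infection-related hospitalizations, ICU admissions, unexpected ED visits and SAEs are reported by period, and infection-related readmission days count in the primary outcome. The prior-failure item is a history variable, and it also counts stopping for an adverse event, which concerns tolerability. SAP 6.2 calls secondary testing exploratory and unpowered.

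Much of this stands. It limits the stakes and weakens the analogy with the history item. It does not settle the point: the SAP never states a treatment-policy target, and separate event tables do not correct the response rate.

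A reader might infer more than the documents support:

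- *That every rescued patient becomes a Complete Response.* Only those whose visit findings meet the rule do.
- *That the rule biases the comparison toward no loss of efficacy.* That needs rescue to be more frequent in the period with the worse true response, which nothing in the documents shows.
- *That response rates are overstated by some known amount.* No rescue frequency is given.
- *That failures are hidden altogether.* The component events are tabulated.
- *That the protocol, too, has no clause for these events.* Its definition is cut off in the text supplied, so one cannot be excluded. The complete SAP derivation has none.

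**Conclusion.** The concern holds in a conditional form. The Appendix B rule can score as Complete Response a patient whose infection worsened and was rescued before the day 10-14 visit, and nothing else in the SAP prevents it. This can overstate response in either period, by 2.3 percentage points per such patient at 43 per period. How many there will be, and whether the two periods differ, are unknown. Usual care and a single post-period dose ("Dalbavancin will be administered as a single IV dose of 1500 mg over 30 minutes") could plausibly lead to different rescue patterns, but the direction cannot be told from the documents. The point affects how a secondary, exploratory efficacy outcome is read. It does not touch the primary result. The change is worth making because it is cheap and the endpoint will be used to judge clinical cost.

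**What to change.** In Appendix B, test for Failure first, in identical words for both periods. Score Failure if, by the day 10-14 visit, any of these occurred:

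1. another antibiotic was substituted or added because the ABSSSI worsened or responded inadequately;
2. an unexpected infection-related major surgery;
3. an infection-related readmission for worsening or recurrence.

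Do not count planned IV-to-oral step-down, culture-directed narrowing, or discontinuation for an adverse event alone. A single dose cannot be discontinued after it is given, so an adverse-event criterion would fall mainly on the pre-period. Apply the existing sign and lesion criteria to the remaining patients, and report the current day 10-14 rule as a sensitivity analysis. Align SAP 4.3 with the result. This classifies outcomes and sets no rule for patient care.

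**Cost.** Mainly derivation wording. Antibiotic use, unexpected surgery and infection-related hospitalizations are already recorded. The adverse event pages can capture worsening of the underlying disease, action taken with the study drug and other treatment given (Protocol 5 and 5.1, SAP 6.2.7).

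**Downsides to state in the SAP.**
- The reason for an antibiotic change must be classified from recorded data, ideally without knowledge of period. SAP 6.2.6 names no reason field for on-study antibiotics, and SAP version 1.0 (09MAY2018) postdates the pre-period interim analysis, so some classification may be retrospective.
- Earlier discharge leaves more time at risk of readmission before the visit, so item 3 may weigh more on the period with shorter stays.
- Reported response rates will be slightly lower.
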